#### Post Treatment Observation Phase

Patients who discontinue study treatment before disease progression has been observed, will undergo disease evaluations every 90 days (+/- 30 days) as specified in the Post-Treatment Observation Phase in the Study Calendar for a duration of 24 months or until confirmed hematologic disease progression, whichever comes first.

## 5. STUDY POPULATION

### 5.1 Inclusion Criteria

Each patient must meet all inclusion criteria listed below to enroll in study:

1. Subject must voluntarily sign and understand written informed consent.
2. Age  $\geq 18$  years at the time of signing the consent form.
3. Histologically confirmed MM
4. Relapsed and/or refractory myeloma defined as follows:
  - i. Relapse or progressive disease after at least one previous line of therapy which must include prior daratumumab. At least 8 doses of daratumumab in a previous line must be administered either as monotherapy or in combination with a daratumumab-free interval of  $\geq 3$  months AND
  - ii. Patient may be daratumumab refractory defined as less than a partial remission (PR) achieved on prior daratumumab-based therapy or have exhibited progression within 60 days of receiving daratumumab. If previous therapy was autologous stem cell transplant (SCT),  $\geq 3$  months must have elapsed after SCT.
5. Measurable disease as defined by  $> 0.5$  g/dL serum monoclonal protein,  $> 0.1$  g/dL serum free light chains,  $> 0.2$  g/24h urinary M-protein excretion, and/or measurable plasmacytoma(s).
6. Must have received prior treatment with both an immunomodulatory drug and proteasome inhibitor in the same or separate lines of therapy.
7. ECOG performance status  $\geq 2$  (Appendix 12.1)
8. Females of childbearing potential (FCBP)† must have a negative serum or urine pregnancy test with a sensitivity of at least 25 mIU/mL within 10 – 14 days prior to and again within 24 hours of prescribing pomalidomide (prescriptions must be filled within 7 days) and must either commit to continued abstinence from heterosexual intercourse or begin TWO acceptable methods of birth control, one highly effective method and one additional effective method AT THE SAME TIME, at least 4 weeks before she starts taking pomalidomide FCBP must also agree to ongoing pregnancy testing. Men must agree to use a latex condom during sexual contact with females of child-bearing potential even if they have had a successful vasectomy. Females must agree not to donate eggs (ova, oocytes) and men not to donate sperm for the purpose of assisted reproduction during the study and for 4 weeks after the last dose of pomalidomide and for 3 months after the last dose of daratumumab. †A female of childbearing potential is a sexually mature woman who: 1) has not undergone a hysterectomy or bilateral oophorectomy; or 2) has not been naturally postmenopausal for at least 24 consecutive months (i.e., has had menses at any time in the preceding 24 consecutive months).
9. Able to take aspirin daily as prophylactic anticoagulation (patients intolerant to ASA may use warfarin or low molecular weight heparin).
10. Life expectancy  $\geq 3$  months
11. Subjects must meet the following laboratory parameters:

- i. Absolute neutrophil count (ANC)  $\geq 750$  cells/mm^3 ( $.75 \times 10^9/L$ )
- ii. Platelets count  $\geq 50,000/mm^3$  ( $50 \times 10^9/L$ )
- iii. Serum SGOT/AST  $\leq 2.0 \times$  upper limits of normal
- iv. Serum SGPT/ALT  $< 3.0 \times$  upper limits of normal (ULN)
- v. Serum CrCl  $\geq 30$  mL/min
- vi. Total bilirubin  $\leq 1.5 \times$  ULN (Total bilirubin  $\geq 1.5 \times$  ULN is acceptable if bilirubin is fractionated and direct bilirubin  $< 35\%$ ).
12. All study participants must be registered into the mandatory POMALYST REMS™ program and be willing and able to comply with the requirements of the POMALYST REMS™ program.

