- Seropositive for hepatitis B (defined by a positive test for hepatitis B surface antigen [HBsAg]). Subjects with resolved infection (ie, subjects who are HBsAg negative but positive for antibodies to hepatitis B core antigen [anti-HBc] and/or antibodies to hepatitis B surface antigen [anti-HBs]) must be screened using real-time polymerase chain reaction (PCR) measurement of hepatitis B virus (HBV) DNA levels. Those who are PCR positive will be excluded EXCEPTION: Subjects with serologic findings suggestive of HBV vaccination (anti-HBs positivity as the only serologic marker) AND a known history of prior HBV vaccination, do not need to be tested for HBV DNA by PCR
  - Seropositive for hepatitis C (except in the setting of a sustained virologic response [SVR], defined as aviremia at least 12 weeks after completion of antiviral therapy).
13. Any serious medical or psychiatric illness that could, in the investigator's opinion, potentially interfere with the completion of treatment according to this protocol.
  14. Known allergy to any of the study medications, their analogues, or excipients in the various formulations of any agent.
  15. Known GI disease or GI procedure that could interfere with the oral absorption or medication tolerance including difficulty swallowing.
  16. Diagnosed or treated for another malignancy within 2 years before study enrollment or previously diagnosed with another malignancy and have any evidence of residual disease. Patients with nonmelanoma skin cancer or carcinoma in situ of any type are not excluded if they have undergone complete resection.
  17. Patient has  $\geq$  Grade 3 peripheral neuropathy, or Grade 2 with pain on clinical examination during the screening period.
  18. Participation in other clinical trials, including those with other investigational agents not included in this trial, within 30 days of the start of this trial and throughout the duration of this trial.
  19. History of thromboembolic event within the past 6 months prior to enrollment.

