## 8. STATISTICAL AND QUANTITATIVE ANALYSES

### 8.1 Statistical Methods

The primary endpoint will be the  $\geq$  VGPR response proportion as best response within the first 8 cycles of treatment. Based on historical data, the  $\geq$  VGPR response proportion is approximately 9%; therefore, the target  $\geq$  VGPR response proportion will be  $\geq$  25%.

This exact single-stage design yields a  $\geq$  0.80 probability of a positive result if the true  $\geq$  VGPR response proportion is  $\geq$  25%. It yields a  $\geq$  0.95 probability of a negative result if the true  $\geq$  VGPR response proportion is  $\leq$  9%. A 95% confidence interval constructed around the expected  $\geq$  VGPR response proportion of 25% can be estimated to be within  $\pm$  17.9% of the observed  $\geq$  VGPR response proportion.

Analysis Plan for Endpoints:

Primary Endpoint:

The primary endpoint is the  $\geq$  VGPR response proportion as best response within the first 8 cycles of treatment; A 95% confidence interval will be estimated for the  $\geq$  VGPR response proportion via binomial proportions.

Secondary endpoints:

Secondary endpoints include median PFS, OS, time to response and progression, DoR, TTNT, ORR, VGPR rate, CR or better rate, improvement in response rate during maintenance therapy and MRD negativity rate. Median PFS/OS, including survival curves, will be estimated using Kaplan-Meier methodology. Greenwood's formula will be used to calculate 95% confidence intervals for the Kaplan-Meier survival estimates.

All analyses will be performed in SAS Version 9.4 (SAS Institute, Inc., Cary, North Carolina) and Stata Version 15.0 (StataCorp, College Station, Texas).

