## 12. APPENDICES

### 12.1 Eastern Cooperative Oncology Group (ECOG) Scale for Performance Status

Grade	Description
0	Normal activity. Fully active, able to carry on all predisease performance without restriction
1	Symptoms but ambulatory. Restricted in physically strenuous activity, but ambulatory and able to carry out work of a light or sedentary nature (eg, light housework, office work)
2	In bed < 50% of the time. Ambulatory and capable of all self-care, but unable to carry out any work activities. Up and about more than 50% of waking hours.
3	In bed > 50% of the time. Capable of only limited self-care, confined to bed or chair more than 50% of waking hours.
4	100% bedridden. Completely disabled. Cannot carry on any self-care. Totally confined to bed or chair
5	Dead

Source: Oken MM, Creech RH, Tormey DC, Horton J, Davis TE, McFadden ET et al. Toxicity and response criteria of the Eastern Cooperative Oncology Group. Am J Clin Oncol 1982; 5 (6):649-55.

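### Inclusion criterion 7 sets ECOG performance status as a lower bound on a scale where higher is worse, so ECOG 0–1 patients are ineligible and there is no ECOG ceiling

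*Combined protocol and SAP*

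**What the plan says.** Criterion 7 in Section 5.1 (Inclusion Criteria) reads "ECOG performance status $\geq 2$ (Appendix 12.1". The list opens with "Each patient must meet all inclusion criteria listed below to enroll in study", so criterion 7 is binding and not descriptive.

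The appendix that it cites, 12.1, defines the scale:

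- Grade 0: "Fully active, able to carry on all predisease performance without restriction".
- Grade 3: "Capable of only limited self-care, confined to bed or chair more than 50% of waking hours".
- Grade 4: "Completely disabled. Cannot carry on any self-care. Totally confined to bed or chair".
- Grade 5 is death.

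Two other eligibility items bear on general fitness. Criterion 10 of Section 5.1 asks for "Life expectancy $\geq 3$ months". Exclusion 13 of Section 5.2 covers "Any serious medical or psychiatric illness that could, in the investigator's opinion, potentially interfere with the completion of treatment". Neither mentions ECOG. The population description in the Protocol Summary says nothing about performance status.

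The statistical design (Sections 8.1 and 8.1.1) rests on fixed rates. The historical ≥ "VGPR response proportion is approximately 9" per cent, the target is 25%, and the regimen is declared worthy of further testing if at least 8 of 40 patients reach VGPR or better.

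**The concern.** An eligibility limit on performance status normally keeps out patients too unwell for the treatment. This one does the opposite: it keeps out the fittest patients and sets no limit at the other end.

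Either way of applying it causes a problem:

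- **Followed literally**, the trial enrols only patients at grade 2 or worse. The rationale, the hypotheses and the sample size say nothing about such a cohort, and it is unclear whether the 9% and 25% rates apply to it. The rule in Section 8.1.7 that stops the study after more than 4 deaths, whatever the enrolment, would also operate in a population that was not considered when the rule was written into the plan.
- **Ignored or silently corrected by sites**, every ECOG 0–1 patient is an eligibility deviation. The full analysis set (Section 8.1.3.2) is defined by treatment received and at least one post-baseline assessment, so these patients stay in the primary analysis. The Protocol Summary lists three enrolling facilities, and they need not all resolve the error in the same way.

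**Working it through.** **1. Criterion against scale.** Applying criterion 7 to each grade in Appendix 12.1:

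| ECOG grade | Meaning on the scale | Passes criterion 7 as printed? |
|---|---|---|
| 0 | Fully active | No |
| 1 | Symptomatic but ambulatory | No |
| 2 | In bed less than half the time | Yes |
| 3 | In bed more than half the time | Yes |
| 4 | Bedridden | Yes |

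All inclusion criteria are mandatory, so a No in the last column makes the patient ineligible. A Yes means only that criterion 7 is met; the other criteria still apply.

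**2. Could the sign be a fault of text extraction?** This is unlikely. Criterion 11 of the same list prints ≤ correctly for AST and total bilirubin, and exclusion 7 in Section 5.2 prints it correctly for toxicity grade.

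**3. Could the restriction be deliberate?** Nothing supports that.

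- The second hypothesis in Section 4.1 concerns early relapse.
- Section 7.5 provides for stem cell collection on study and for transplant after 6 cycles.
- Section 5.2 excludes serious cardiac and obstructive airway disease.
- No rationale, sample-size assumption or planned analysis refers to a poor-performance cohort.

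**4. Does the error touch the design arithmetic?** Inputs from Section 8.1.1: n = 40, success if X ≥ 8, p0 = 0.09, p1 = 0.25. The exact binomial tail is

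P(X ≥ 8 | p) = Σ (k = 8 to 40) C(40, k) p^k (1 − p)^(40 − k).

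- At p = 0.09 it is 0.0242, so the probability of a negative result is 1 − 0.0242 = 0.9758. The plan claims at least 0.95.
- At p = 0.25 it is 0.818. The plan claims at least 0.80.

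The plan's figures are reproduced. ECOG does not enter the formula, so correcting the sign changes neither n nor the cut-off.

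**5. What if the planning rates do not fit the enrolled cohort?** The documents give no response rates by ECOG, so the true rates below are assumptions. They show only how sensitive the fixed rule is:

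| Assumed true ≥VGPR rate | P(X ≥ 8 of 40) |
|---|---|
| *Without added benefit* | |
| 5% | 0.0007 |
| 6% | 0.002 |
| 9% (plan) | 0.024 |
| 12% | 0.100 |
| 15% | 0.244 |
| *On D-ClaPd* | |
| 20% | 0.563 |
| 22% | 0.680 |
| 25% (plan) | 0.818 |

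The rule behaves as designed only if the 9% and 25% rates suit the patients who are enrolled. The table does not say which row would apply.

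**The case against.** The strongest reply is that this is an obvious typographical slip, that any experienced site will read it the other way, and that the design is untouched. Most of this can be granted. The sign is probably inverted, literal enrolment of only ECOG 2-or-worse patients is the less likely outcome, and the design figures stand. But the reply concedes the deviation problem: an eligibility rule that sites have to disregard in order to run the trial is still wrong as written.

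Four stronger readings are tempting, and the documents do not support them:

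- *The historical benchmarks cannot describe the enrolled population.* The background (Section 1.1) describes the pomalidomide/dexamethasone phase 3 and ClaPd phase 2 cohorts by prior lines and refractoriness and gives no ECOG limit or distribution. Comparability on performance status cannot be checked, which is less than saying it fails.
- *Response would fall and early deaths would rise.* The documents contain no response or survival data by ECOG grade, so neither the direction nor the size can be derived.
- *Most of the 40 patients would be affected.* If 70% to 90% of candidates were ECOG 0–1, the count would be 0.70 × 40 = 28 to 0.90 × 40 = 36. Nothing in the documents anchors that range, and the point does not need it.
- *Bedridden patients are eligible.* They pass criterion 7 only. The life-expectancy criterion and exclusion 13 limit frailty indirectly, and neither makes an ECOG 0–1 patient eligible.

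**Conclusion.** Criterion 7 is wrong as written and must be corrected. The conclusion needs only the printed inequality, the direction of the scale it cites, and the rule that every inclusion criterion must be met. That the sign is reversed is an inference from the rest of the protocol. It is a probable one, but the sponsor has to confirm it.

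The certain consequence is that each ECOG 0–1 patient is either turned away or enrolled in breach of the protocol. If the rule is followed literally, the suitability of the 9% and 25% rates is in doubt, by an amount and in a direction that the documents do not allow anyone to state. The sample size of 40 and the cut-off of 8 are not in question on this point.

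**What to change.** The sponsor should confirm the intended ECOG limit and reconcile criterion 7 with Appendix 12.1 by printing the limit in the correct direction, as an upper bound if that is the intent. Any eligibility checklist or CRF check should be compared with the corrected text. Those materials are not part of the documents, so whether they carry the same error is unknown.

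If patients have already been enrolled, their screening ECOG grades, which the Schedule of Study Procedures collects, should be listed so that deviations from the printed rule can be documented and explained.

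The cost is a minimal amendment to one criterion and a consistency check. The sample size, decision rule and analysis do not change.

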## 5.2 Exclusion Criteria

Patients meeting any of the following exclusion criteria are not to be enrolled in the study:

1. Prior exposure to non-daratumumab anti-CD38 monoclonal antibodies. Prior pomalidomide exposure in 1 or more previous lines of therapy allowed if partial remission (PR) or better achieved. No disease progression may have occurred within 60 days of receiving pomalidomide.
2. Clinically significant cardiac disease defined by any of the following criteria:
  1. New York Heart Association (NYHA) Class III or IV heart failure
  2. Unstable cardiac arrhythmia
  3. Unstable angina
  4. Myocardial infarction within the past 6 months.
3. Baseline prolongation of the QT interval (men  $> 450$  ms; women  $> 470$  ms), on concurrent drugs known to prolong the QT interval (see Appendix 12.3), or with ongoing proarrhythmic conditions.
4. Severe obstructive airway disease defined by forced expiratory volume at one second (FEV1)  $< 50\%$ .
5. Planned high-dose chemotherapy and autologous stem cell transplantation within 6, 28-day treatment cycles after starting on treatment.
6. Female patients who are lactating or have a positive serum pregnancy test during the screening period.
7. Failure to have fully recovered (ie,  $\leq$  Grade 1 toxicity) from the reversible effects of prior chemotherapy.
8. Major surgery within 14 days before enrollment.
9. Radiotherapy within 14 days before enrollment. If the involved field is small, 7 days will be considered a sufficient interval between treatment and study drug administration.
10. Infection requiring systemic intravenous antibiotic therapy or other serious infection within 14 days before study enrollment.
11. Systemic treatment, within 14 days before the first dose, with strong CYP3A inducers (rifampin, rifapentine, rifabutin, carbamazepine, phenytoin, phenobarbital, see Appendix 12.4), or use of Ginkgo biloba or St. John's wort.
12. Ongoing or active systemic infection including
  - Seropositive for human immunodeficiency virus (HIV)

- Seropositive for hepatitis B (defined by a positive test for hepatitis B surface antigen [HBsAg]). Subjects with resolved infection (ie, subjects who are HBsAg negative but positive for antibodies to hepatitis B core antigen [anti-HBc] and/or antibodies to hepatitis B surface antigen [anti-HBs]) must be screened using real-time polymerase chain reaction (PCR) measurement of hepatitis B virus (HBV) DNA levels. Those who are PCR positive will be excluded EXCEPTION: Subjects with serologic findings suggestive of HBV vaccination (anti-HBs positivity as the only serologic marker) AND a known history of prior HBV vaccination, do not need to be tested for HBV DNA by PCR
  - Seropositive for hepatitis C (except in the setting of a sustained virologic response [SVR], defined as aviremia at least 12 weeks after completion of antiviral therapy).
13. Any serious medical or psychiatric illness that could, in the investigator's opinion, potentially interfere with the completion of treatment according to this protocol.
  14. Known allergy to any of the study medications, their analogues, or excipients in the various formulations of any agent.
  15. Known GI disease or GI procedure that could interfere with the oral absorption or medication tolerance including difficulty swallowing.
  16. Diagnosed or treated for another malignancy within 2 years before study enrollment or previously diagnosed with another malignancy and have any evidence of residual disease. Patients with nonmelanoma skin cancer or carcinoma in situ of any type are not excluded if they have undergone complete resection.
  17. Patient has  $\geq$  Grade 3 peripheral neuropathy, or Grade 2 with pain on clinical examination during the screening period.
  18. Participation in other clinical trials, including those with other investigational agents not included in this trial, within 30 days of the start of this trial and throughout the duration of this trial.
  19. History of thromboembolic event within the past 6 months prior to enrollment.

## 6. STUDY DRUG

### 6.1 Description of Investigational Agents

#### 6.1.1 Daratumumab

Daratumumab SC drug product for oncology/hematology is a colorless to yellow liquid. The final daratumumab SC product is daratumumab at a target concentration of 120 mg/mL co-formulated with rHuPH20 in a 25R vial at a nominal fill to deliver 15 mL. As a bridging strategy, administration of daratumumab by the SC route was after mixing the daratumumab IV drug product with rHuPH20 in polypropylene syringes. Refer to the Halozyme rHuPH20 Investigator's Brochure for details.

Daratumumab SC drug product for oncology/hematology is co-formulated at a concentration of 120 mg/mL daratumumab with 2000 U/mL rHuPH20 in an isotonic buffer consisting of histidine, sorbitol, methionine, NaCl and polysorbate 20 at pH 5.6.

For additional details, please see the daratumumab package insert.

#### 6.1.2 Pomalidomide Capsules

Pomalidomide is supplied as dark blue opaque cap and yellow opaque body, imprinted “POML” on the cap in white ink and “1 mg” “2 mg” “3 mg” or “4 mg” on the body in black ink.

Store at 20°C-25°C (68°F-77°F); excursions permitted to 15°C-30°C (59°F-86°F). [see USP Controlled Room Temperature].

Care should be exercised in handling of pomalidomide. Pomalidomide capsules should not be opened or crushed.

If powder from pomalidomide contacts the skin, wash the skin immediately and thoroughly with soap and water. If pomalidomide contacts the mucous membranes, flush thoroughly with water. Follow procedures for proper handling and disposal of anticancer drugs.

### 6.2 Study Drug Administration

All protocol-specific criteria for administration of study drug must be met and documented before drug administration. Study drugs will be administered or dispensed only to eligible patients under the supervision of the investigator or identified sub-investigator(s). Patients should be monitored for toxicity, as necessary, and doses of daratumumab, pomalidomide, and dexamethasone should be modified or delayed as needed to accommodate patient tolerance to treatment (See Section 6.3).

#### 6.2.1 Daratumumab Administration

The daratumumab vials should be stored in the original carton in a refrigerator at 2°C to 8°C and must not be utilized after the expiry date printed on the label. The product must be protected from light and must not be frozen. Since daratumumab does not contain preservatives, any unused portion remaining in the vial must be discarded.

Refer to the Halozyme rHuPH20 Investigator’s Brochure for details on storage and handling of rHuPH20.

Daratumumab 1800 mg SC is to be administered as described in the Study Calendar.

Injections may be performed as outpatient or inpatient visits, depending on local clinical practice. Patients will receive pre-medications and post-medications as outlined in Section

6.2.1.3. Daratumumab (1800 mg) will be administered by SC injection by manual push over approximately 3 - 5 minutes in the abdominal subcutaneous tissues in left/right locations, alternating between individual doses. The volume of the SC solution will be 15 mL for the 1800 mg dose. Refer to the Investigational Product Preparation Instructions (IPPI) for additional guidance on SC administration of Dara-SC. Vital signs should be monitored before, during, and after the first injection of daratumumab on Cycle 1 Day 1 and Cycle 1 Day 8. For all other doses, vital signs should be measured immediately before and after the injection. The median time to onset of IRRs for daratumumab SC is over 3 hours. Thus, all subjects must be observed for at least 6 hours after the end of the SC injection during Cycle 1 Day 1 and, if deemed necessary by the investigator, after subsequent injections. Reasons for continued observation on subsequent daratumumab injections may include but are not limited to the following: subjects with a higher risk of respiratory complications (eg, subjects with mild asthma or subjects with COPD who have an FEV1 <80% at screening or developed FEV1 <80% during the study without any medical history), subjects with IRR with first injection of study drug, subject with a decreased condition on day of dosing compared to prior dosing day. The dose of daratumumab will remain constant throughout the study.

